4.4 Interim Analyses and Data Monitoring

No interim analyses are planned for this study.

An independent DMC is established for this study to provide the SC and the sponsor with recommendations related to the protection of the subjects safety, including stopping recruitment and study treatment. For that purpose, the DMC will regularly review all incidences of serious adverse events and adverse events of special interest. Organizational aspects, responsibilities, and processes are described in the DMC charter [5].

At least one DMC meeting per year will be held to review the subjects enrolled. In any case one DMC meeting will take place when the first 5 subjects of the age cohort (≥ 12 to < 18 years) finish the main treatment phase and have reached their optimal dose and received this dose until assessment of their first control X-ray of left hand at week 24. After this DMC meeting, the DMC will give recommendations to the SC whether to continue with enrolment in this age cohort and open enrollment in the subsequent lower age cohort (≥ 6 to < 12 years). Only after obtaining positive safety and efficacy data in the first 5 patients, enrolment in the group from 6 to less than 12 years of age will be started. The subsequent meetings are planned to occur when additional 5 patients, independently of age cohort, finish the main treatment period.

For all subjects reaching week 24 of the main study treatment period and all subjects continuing in the LTE, the left hand X-rays is evaluated by the DMC. The DMC is provided with all relevant documentation on an ongoing basis including all cases of clinical worsening (as defined in protocol section 6.3) that occur after intake of first dose of study medication, in the main study treatment period - including the 60 day safety follow-up period (only for those patients not entering the LTE).

The mock-ups for the DMC outputs are described within relevant sections of this SAP. A separate DMC SAP is not foreseen.

4.5 Data Rules

Unless otherwise specified, baseline is the last available non-missing value prior and up to the time of the first intake of study medication, i.e. first dose of riociguat. Change from baseline is calculated as the value at the post-baseline time point minus the baseline value, i.e. value at time point – value at baseline.

Post-treatment values will be considered treatment-emergent if they start within 2 calendar days after the last day of study drug administration, i.e. the treatment-emergent window will be 2 days.

All data from the electronic case report form (eCRF) will be organized and analyzed according to the scheduled visits. Any additional or unscheduled measurements will be included in the listings according to the date/time of assessment. In the case of multiple observations at a specific visit, the observation that is closest to the target visit will be used in the analyses. If observations have the same distance (before and after) to the target visit, the latest one will be used. If the repeated measurements are all taken on the same day, then the last measurement will be used.

Subgroup analyses will be performed by age cohort (≥ 6 to < 12 years and ≥ 12 to < 18 years) and by concomitant PAH medication (ERA only, ERA + PCA, PCA only) specified at Screening. The patients are assigned to the concomitant PAH medication groups specified before date of treatment according to Standardised Drug Grouping (SDG)/Bayer Drug Groupings (BDG), section 6.1.6. Patient’s assignment to PAH medication grouping is depicted in Table 4–1:

Table 4–1: Concomitant PAH medication grouping

Group	SDG (BDG)	
	Endothelin receptor antagonists	Prostacyclins (including analogues and receptor agonists)
ERA only	Yes	No
ERA + PCA	Yes	Yes
PCA only	No	Yes

Listings will be sorted by subject identifier, visit (if applicable), date and time.

Dates will be formatted as DDMMYYYY. Partial dates will be presented on data listings with dashes for the missing parts, e.g. like --MMYYYY. Listing should only present the collected dates, not imputed dates.

Rounding for all variables will occur only as the last step, immediately prior to presentation in listings and tables. No intermediate rounding will be performed on derived variables. The standard rounding practice of rounding numbers ending in 0-4 down and numbers ending 5-9 up will be employed.

Every table, listing and figure will be produced with an electronic date stamp to document when it was produced.

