### **Laboratory parameters**

Laboratory parameters will be collected at V0 (if no historical data is available), V5 and V9.

Hematology: CBC

General Chemistry: AST, ALT, Creatinine, BUN, GGT, UA, T-Bil, Alb, Na, K, Ca, and P

Afterwards; any additional collection of laboratory parameters will be obtained in case medically required according to a local package insert of bosentan, or other ERA, or medical practice at the site at any time point and will be captured in the eCRFs.

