#### 7.4.1 Safety analysis - amended

The primary objective is to evaluate the safety and tolerability of riociguat in children with PAH. Primary endpoint of the study is: Change from baseline to end of treatment (week 24) of safety and tolerability assessed by incidence of adverse events and serious adverse events, recording of vital signs and left-hand X-ray and laboratory panel.

The safety evaluation of adverse event (AE) data will include:

- The incidence of treatment-emergent AEs (TEAEs). Adverse events are considered to be treatment-emergent if they have started or worsened after first application of study drug up to 2 days after end of treatment with study drug.
- Tables of serious and/or drug-related treatment-emergent AEs, treatment-emergent AEs leading to discontinuation of study drug and AEs of special safety interest.

- The incidence of AEs during pre-treatment and during follow-up (i.e. AEs occurring more than 2 days after end of treatment with study drug).
- Listings of serious adverse events (SAEs), AEs leading to discontinuation of study drug and AEs of special safety interest.
- Descriptive summaries of mortality in the study.
- Listing of deaths in the study period, including day of death relative to start and stop of study drug and cause of death.

The safety evaluation of laboratory data will include:

- Incidence rates of treatment-emergent laboratory values outside of normal range
- Incidence rates of pre-specified laboratory data abnormalities
- Descriptive analysis of laboratory parameters (AST, ALT, BUN, creatinine, GGT, UA, T-Bil, Alb, Na, K, Ca, P, and CBC) and their corresponding changes from baseline

Other evaluations of safety data will include:

- Descriptive analysis of body weight, vital signs, ECG parameters, left hand x-ray and their corresponding changes from baseline.
- Tabulation of ECG status pre-dose, 2 and 4 hours post treatment-initiation.
- Incidence rates of treatment-emergent ECG abnormalities.

Time points of assessment: Assessment of adverse events at baseline, at all visits in the titration phase and maintenance phase, and every 3-4 months in the extension phase. Left hand x-ray at baseline, end of study treatment period (week 24) and every 12 months until growth plates are closed.

For details on safety variables, see section 6.2.

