4.3 Handling of Missing Data

All missing or partial data will be presented in the subject data listing as they are recorded on the electronic case report form (eCRF). Missing data proportions will be reported.

In general they will not be substituted or replaced, except for the parameters described below.

General rules

- **Efficacy variables**

Last visit is defined as last observed value post-baseline (including unscheduled visits, but not including follow-up), if not specified otherwise.

- **6 Minute Walking Distance**

If a subject dies before Week 24 or during follow-up after termination before Week 24, the worst value = 0 is used.

- WHO Functional Class

If a subject dies before Week 24 or during follow-up after termination before Week 24, the worst value = IV (4) is used.

- **Safety variables**

Last visit is defined as last observed value post-baseline (including unscheduled visits, but not including follow-up), if not specified otherwise.

Treatment emergent events, phases, period and relative days will be derived according to standard guidelines.

A complete date is not needed for the statistical tables, but an imputation on the phase of the study for adverse events and concomitant medications (pre, during or post) is required. The 'minimum' rule will be used for start dates which is first day of month or 1st of January. The 'maximum' rule will be used for end dates which is last day of month or 31st of December.

- **Child Health Questionnaire (SF-10)**

Scores will be provided by QualityMetric Score was generated by QualityMetric.

- **Pediatric Quality of Life Inventory™ (PedsQL™)**

In the case of missing single questionnaire items, the missing data rules in the scaling and scoring document will be followed. Specifically, if more than 50% of the items in the scale are missing, the Scale Scores should not be computed. If 50% or more items are completed: Impute the mean of the completed items in a scale.

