5.1 Assignment of analysis sets

Final decisions regarding the assignment of subjects to analysis sets will be made during the VRM and documented in the VRR (see section 4.6).

Safety analysis set (SAF)

A subject will be included in the SAF (equivalent to full analysis set, FAS) if he/she is assigned to receive study medication and has received at least one dose of the study medication.

Listing only set (LOS)

All subjects who signed informed consent for treatment eligibility at screening but could not be assigned to safety analysis set defined above. Their data will be presented in individual subject data listings in CSR section 16.2.1 and will not be included in any statistical analyses.

6. Statistical Methodology

The analysis will include data from screening to week 24. Information collected at safety follow-up visit, for subjects not continuing in the LTE phase, will be included in tables, if applicable. LTE phase data collected until the cut-off date from subjects already in the LTE phase will be listed only.

The cut-off date will be defined after all treated subjects completed the 24 week treatment period assessments or safety follow-up visit is completed for all subjects who are not continuing in the LTE phase, except those who are lost to follow-up. The cut-off date will be defined by the sponsor, allowing time for data cleaning.

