6.4.2 Laboratory data

Following laboratory parameters are collected: complete blood count (CBC) of hematology parameters and general chemistry parameters Creatinine, SGOT/AST, SGPT/ALT, blood urea nitrogen (BUN), gamma-glutamyltransferase (GGT), uric acid, total bilirubin, albumin, sodium, potassium, calcium, phosphate and glomerular filtration rate (calculated based on Schwartz formula for non Japan population and Japan-specific formula for Japan population). All data will be evaluated via local laboratory. Descriptive analysis of laboratory parameters (AST, ALT, BUN, creatinine, GGT, uric acid, total bilirubin, albumin, sodium, potassium, calcium, phosphate, CBC and Glomerular filtration rate) and their corresponding changes from baseline will be presented. Values that are outside the labor specific reference ranges will be considered as laboratory abnormality.

Data will be summarized by visit using frequency tables for values within/outside reference ranges. Laboratory data outside the standard reference ranges and clinically relevant abnormal laboratory values will be flagged in listings.

Laboratory data will be presented overall (all ages).

Additionally a table of Treatment emergent specific laboratory abnormalities will be produced including SGOT/AST > 3*ULN, SGPT/ALT > 3*ULN, Bilirubin > 2*ULN, Glomerular filtration rate <30 mL/min/1.73m².

Laboratory data are part of the DMC package.

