6.4.3 Pregnancy test

Results of the pregnancy tests (urine or serum) will be listed only.

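### The SAP does not say that unscheduled laboratory values count towards the incidence of treatment-emergent abnormalities, and as written its data rules leave them to listings

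*SAP*

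**What the plan says.** SAP 4.5 sets the general rule: "All data from the electronic case report form (eCRF) will be organized and analyzed according to the scheduled visits". The next sentence deals with everything else: "Any additional or unscheduled measurements will be included in the listings according to the date/time of assessment".

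SAP 6.4.2 says of laboratory results: "Data will be summarized by visit using frequency tables for values within/outside reference ranges". It then adds a separate treatment-emergent table at fixed thresholds: AST or ALT above 3×ULN, bilirubin above 2×ULN, and GFR below 30 mL/min/1.73 m². That table is not described as by visit, and the SAP does not say which values feed it.

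SAP 4.3 gives one analytic use of unscheduled values, stated for safety and for efficacy variables alike: "Last visit is defined as last observed value post-baseline (including unscheduled visits, but not including follow-up), if not specified otherwise".

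Protocol 7.4.1 plans "Incidence rates of treatment-emergent laboratory values outside of normal range", together with incidence rates for pre-specified laboratory abnormalities. Neither is limited to scheduled visits. Protocol 6.2 (Laboratory parameters) schedules tests at V0, V5 and V9. Beyond those, "any additional collection of laboratory parameters will be obtained in case medically required", following the local bosentan or other ERA package insert or site practice, and the results go into the eCRF. The flow chart and protocol 6.1.3 add a laboratory draw at the end-of-treatment visit for children who leave between V1 and V9.

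**The concern.** An incidence asks whether a child had the abnormality at any time on treatment. A by-visit table asks how many children were abnormal at week 8 and how many at week 24. Protocol 7.4.1 plans the first. SAP 4.5, with no exception in 6.4.2, leads a programmer to build the second, and possibly to build the threshold table from scheduled values too.

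The direction of the error is known. A child counts if any eligible value is abnormal, so shrinking the set of eligible values can lower the count but never raise it. The values set aside may also be the informative ones, since some unscheduled tests will be prompted by a suspected problem. Laboratory parameters belong to the primary safety outcome in protocol 6.2 and 7.4.1 and to the safety assessment in SAP 6.4, although the synopsis omits them from its primary variable.

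**Working it through.** The plan gives no figure to reproduce. The study is single-arm and descriptive, and protocol 7.5 states no formal sample size calculation. The check is therefore of the text, followed by an illustration of size.

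**1. Following one value through the rules.** Take a hypothetical ALT above 3×ULN at week 14, drawn under an ERA package insert, and normal again at week 24.

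- eCRF: recorded (protocol 6.2).
- By-visit range table (SAP 6.4.2): absent, because only V5 and V9 carry scheduled on-treatment tests.
- Last-visit value (SAP 4.3): absent, because the last value is the normal one at week 24.
- Specific-abnormality table (SAP 6.4.2): not stated; absent if the general rule in 4.5 is applied.
- Listing: present and flagged (SAP 4.5, 6.4.2).
- Adverse event tables: present only if the abnormality meets the reporting conditions of protocol 8.5, for example if the investigator judges it relevant.

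**2. How often a scheduled draw would find the abnormality.** Draws are at weeks 8 and 24, with a longest gap of 24 − 8 = 16 weeks. Assumptions not in the documents: onset uniform over weeks 0 to 24, fixed duration D of at most 8 weeks, and the child on treatment and tested on schedule. The abnormality is present at a draw if onset falls in [8 − D, 8] or [24 − D, 24]. These intervals do not overlap for D ≤ 8, so P = 2D/24.

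- D = 2 weeks: 4/24 = 17%
- D = 4 weeks: 8/24 = 33%
- D = 8 weeks: 16/24 = 67%

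The remaining 83%, 67% and 33% would miss both draws. How many of these were found by an unscheduled test depends on local testing frequency, which the documents do not give.

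**3. What one child is worth.** At 20 children, the minimum number on an ERA, one child is 1/20 = 5 percentage points. Exact 95% intervals: 0/20 gives 0 to 16.8%; 1/20 gives 0.1 to 24.9%; 2/20 gives 1.2 to 31.7%.

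**4. Blood pressure for comparison.** After baseline, vital signs are scheduled at weeks 2, 4, 6, 8, 12, 16, 20 and 24. On the same model a 2-week episode spans a visit with probability 8 × 2/24 = 67%. A 4-week episode always does, since the longest gap is 4 weeks. The sparse-sampling argument applies to laboratory tests and only weakly to blood pressure.

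**The case against.** The strongest reply is that the SAP never confines unscheduled values to listings. Where it means that, it says so: "Results of the pregnancy tests (urine or serum) will be listed only" and "LTE phase data collected until the cut-off date from subjects already in the LTE phase will be listed only". SAP 4.5 lacks that restriction, and SAP 4.3 uses unscheduled values in the last-visit definition. The threshold table is introduced separately, is not called by visit, and rests on a treatment-emergent window counted in days. Displays also follow sponsor standards that are not part of these documents. All of this stands: for the threshold table the SAP is silent, not exclusionary. Silence still leaves the general rule of 4.5 as the default, and the last-visit rule does not recover an abnormality that has resolved.

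The second reply is that important events are counted elsewhere. A reader might infer that liver and blood-pressure abnormalities found between visits vanish from the primary safety tables. The documents do not support that. Protocol 8.5 makes clinically relevant laboratory abnormalities adverse events, protocol 8.8 makes symptomatic hypotension an event of special interest, and both reach the tables of SAP 6.4.1 whatever the visit. A reader might also infer that the DMC would not see such values. SAP 6.4.2 flags out-of-range results in listings and puts laboratory data in the DMC package. These points limit the consequence but do not remove the gap: adverse event reporting depends on judgement, whereas a fixed threshold table counts every child who crosses the limit.

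Third, weeks 8 and 24 are not the only scheduled draws. A child withdrawn early, for instance for a liver elevation, has the end-of-treatment test. That is correct, and it leaves children who stay on treatment unaffected.

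**Conclusion.** The point holds for the laboratory incidence tables and should be fixed. The range table in SAP 6.4.2 is by visit where protocol 7.4.1 plans an incidence, and the SAP does not say whether unscheduled values enter the specific-abnormality table. A transient abnormality found between draws can go uncounted in both unless it is also reported as an adverse event.

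The size rests on the uniform-onset and fixed-duration assumptions above. The coverage of 17% to 67% describes scheduled draws alone. It is not an estimate of how many abnormalities will be lost, which depends also on how often unscheduled tests are done and on adverse event reporting. With about 20 children even one omission is visible, although no hypothesis test depends on it.

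Two further inferences are not supported. The protocol has medically required tests recorded in the eCRF, but no sentence says they are collected to feed a particular table. And there is no matching protocol–SAP conflict for blood pressure: protocol 7.4.1 asks for descriptive vital signs and changes from baseline, not an incidence of low systolic pressure.

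**What to change.** In SAP 4.5 and 6.4.2:

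- Keep by-visit summaries, including changes from baseline, on scheduled values.
- State that the incidence of out-of-range values and of the specific abnormalities (AST, ALT, bilirubin, GFR) uses every value after first dose up to 2 days after last dose, scheduled or unscheduled. This is the treatment-emergent window that SAP 4.5 already defines.
- Count each child once per parameter, by the worst value.

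The worst-value rule also settles repeat tests. Under SAP 4.5 the value closest to the target visit, or the last on the same day, is used, so an abnormal result followed by a normal repeat could otherwise be lost.

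An any-time row for lowest systolic pressure in SAP 6.4.4 is optional.

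The cost is a few sentences and minor programming before database lock, with no new data. Reported rates may be slightly less favourable. An any-time rate also depends on how often each child was tested, so a footnote giving the number of unscheduled values used would help interpretation.

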4.6 Validity Review

Validity Review Meeting (VRM) will be performed according to applicable Syneos Health Standard Operating Procedures (SOP) and will be led by the Syneos Health Lead Data Manager. Details are available in the data management plan (DMP).

The results of the VRM will be documented in the Validity Review Report (VRR) and may comprise decisions and details relevant for statistical evaluation. Any changes to the statistical analysis prompted by the results of the validity review meeting will be documented in an amendment and, if applicable, in a supplement to this SAP.

All protocol deviations will be listed. All important deviations will be summarized by age cohort and concomitant PAH medication.

5. Analysis Sets

5.1 Assignment of analysis sets

Final decisions regarding the assignment of subjects to analysis sets will be made during the VRM and documented in the VRR (see section 4.6).

Safety analysis set (SAF)

A subject will be included in the SAF (equivalent to full analysis set, FAS) if he/she is assigned to receive study medication and has received at least one dose of the study medication.

Listing only set (LOS)

All subjects who signed informed consent for treatment eligibility at screening but could not be assigned to safety analysis set defined above. Their data will be presented in individual subject data listings in CSR section 16.2.1 and will not be included in any statistical analyses.

6. Statistical Methodology

The analysis will include data from screening to week 24. Information collected at safety follow-up visit, for subjects not continuing in the LTE phase, will be included in tables, if applicable. LTE phase data collected until the cut-off date from subjects already in the LTE phase will be listed only.

The cut-off date will be defined after all treated subjects completed the 24 week treatment period assessments or safety follow-up visit is completed for all subjects who are not continuing in the LTE phase, except those who are lost to follow-up. The cut-off date will be defined by the sponsor, allowing time for data cleaning.

6.1 Population characteristics

Demographic and baseline characteristics of subjects will be summarized using descriptive statistics.

The variables to profile the study population include demographic data, medical history, concomitant PAH specific medication. If not stated otherwise, population characteristics will be tabulated overall. The actual body-weight adjusted dosing information will be included in the listings as applicable (e.g. where the collected data could be assigned to the treatment dose).

6.1.1 Inclusion-/Exclusion criteria

Data from the assessment of inclusion and exclusion criteria will be presented in listings for all subjects who signed informed consent/assent and failed the inclusion/exclusion criteria.

